### **8.1.2.3 Definition of an Unexpected Adverse Event**

An unexpected adverse event is defined as any adverse drug experience, the specificity or severity of which is not consistent with the current Investigator Brochure; or, if an Investigator Brochure is not required or available, the specificity or severity of which is not consistent with the risk information described in this protocol or in the regulatory agency study authorization application.

Unexpected, as used in this definition, refers to an adverse drug experience that has not been previously observed (e.g., included in the Investigator's Brochure) rather than from the perspective of such experience not being anticipated from the pharmacological properties of the pharmaceutical product.

### **8.1.2.4 Serious Adverse Event (SAE)**

A serious adverse event is defined as any untoward medical occurrence that at any dose:

1. Results in death,
2. Is life-threatening (i.e., the patient was at risk of death at the time of the event. It does not refer to an event which hypothetically might have caused death if it was more severe),
3. Requires in-patient hospitalization or prolongation of existing hospitalization excluding that for pain management, disease staging/re-staging procedures, or catheter placement unless associated with other serious events,
4. Results in persistent or significant disability/incapacity, or
5. Is a congenital anomaly/birth defect.

Important medical events that may not result in death, be life-threatening, or require hospitalization may be considered serious adverse drug events when, based on appropriate medical judgment, they may jeopardize the patient and may require medical or surgical intervention to prevent one of the outcomes listed above.

Disease Progression, or death as a result of disease progression, **are not considered to be SAEs**. However, if the progression of the underlying disease is greater than what would normally be expected as part of the natural course of the disease under study for the patient, or if the Investigator considers that there was a causal relationship between treatment with study drug or protocol design/procedures and the disease progression, then it must be reported as an SAE.

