#### DLT excludes:

- Hematological and non-hematological  $\leq$  Grade 2 unless considered non-acceptable.
- Other Grade 3 self-limited or medically controllable toxicities (e.g., fever without  $\geq$  Grade 3 neutropenia, lymphopenia, nausea, vomiting, diarrhea, fatigue). Note, such events are considered DLT if the abnormality leads to hospitalization or the abnormality persists for  $>72$  hours despite appropriate interventions (e.g., replacement therapy for electrolyte abnormalities, when indicated).
- Electrolyte disturbances that are managed to Grade 1 or less with supplemental therapy.

Any adverse event that is potentially related to PTX-35 and requires discontinuation of treatment should be considered a DLT. A DLT will be considered related to PTX-35 treatment unless there is a clear, well-documented relation to intercurrent illness or primary malignant disease. AEs that meet the above criteria but occur after the DLT evaluation period will not be defined as DLTs but will be reported as AEs/Serious Adverse Events (SAEs), as applicable, and will be reviewed across all cohorts during the study to help inform dose escalation decisions.

In case of suspicion of a DLT, the Investigator must inform the Medical Monitor/Sponsor immediately. The DLT will be confirmed by the Medical Monitor/Sponsor and a decision must be taken by the Sponsor regarding if an *ad hoc* SRC meeting is required.

Patients who discontinue therapy before completion of 2 cycles (DLT period) for other reasons than dose-limiting toxicity will be replaced. Patients who are tolerating PTX-35 will not have to discontinue study treatment prematurely due to the occurrence of DLTs in another patient in the same cohort, unless decided by the SRC.

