### **6.3 Dose Modification and Management of Immune-Related Adverse Events, Infusion Reactions, and Cytokine Release Syndrome**

One level dose reduction per the dose escalation scheme, for toxicity is allowed. If the toxicity is equivalent to a DLT (see Section 6.1.3) then continued treatment at a lower dose level needs approval by the sponsor and/or SRC.

If immune related adverse events occur, these should be managed according to the ASCO2018 guideline for immune checkpoint inhibitors, and therapy should be continued with close monitoring for Grade 1 toxicities, with the exception of some neurologic, hematologic, and cardiac toxicities. For Grade 2 toxicities, corticosteroids may be administered, and dose should be held until resolution of the AE. Grade 3-4 toxicities treatment with PTX-35 should be discontinued and treatment with high-dose corticosteroids initiated.

All patients should be observed for infusion-related reactions (e.g., back pain, fever and/or shaking chills, flushing and/or itching, alterations in heart rate and blood pressure, dyspnea or chest discomfort, skin rashes, or anaphylaxis). For Grade 1-2 reactions, the infusion should be temporarily interrupted and then resumed when symptoms are resolved. If symptoms have not resolved in 15 minutes treatment with acetaminophen and/or antihistamines may be administered per institutional standard at the discretion of the investigator. Premedication prior to subsequent doses is allowed and should be considered. Grade 3 or 4 infusion related reactions should be managed per institutional standards (e.g., IM epinephrine, followed by IV diphenhydramine and ranitidine, and IV glucocorticoid), and treatment with PTX-35 should be permanently discontinued.

Cytokine release syndrome (CRS) is associated with elevated circulating levels of several cytokines including interleukin (IL)-6 and interferon  $\gamma$ , and uncontrolled studies demonstrate that immunosuppression using tocilizumab, an anti-IL-6 receptor antibody, with or without corticosteroids, can reverse the syndrome. However, because early and aggressive immunosuppression could limit the efficacy of the immunotherapy, current approaches seek to limit administration of immunosuppressive therapy to patients at risk for life-threatening consequences of the syndrome. The treatment algorithm suggested by Lee et al outlined in Figure 4 should be used to manage such reactions.

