### **8.1.2.6 Reporting of Serious Adverse Events**

Adverse events classified as serious require expeditious handling and reporting to Sponsor or its designee to comply with regulatory requirements.

For any serious adverse event (SAE) that occurs while a patient is on-study; within 30 days of the last study drug administration, regardless of any opinion as to the relationship of the SAE to the study drug; or if any SAE that the Investigator feels is related to the study drug occurs later than 30 days after the last study drug administration, the Sponsor or its designee must be notified immediately (within 24 hours of becoming aware of the event).

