## 9.2 Endpoints

### 9.2.1 Primary

- Number of Dose-limiting toxicities (DLTs) per NCI CTCAE v5.0.
- Frequency of treatment-emergent adverse events (TEAEs) and serious adverse events (SAEs) related to PTX-35 during the trial.

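### The SAE definition excludes admissions for pain management with no causality limit, so a PTX-35-related admission for pain alone is not an SAE by default

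*Combined protocol and SAP*

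**What the plan says.** Section 8.1.2.4 lists five SAE criteria. The third, inpatient or prolonged hospitalization, carries an exclusion: "excluding that for pain management, disease staging/re-staging procedures, or catheter placement unless associated with other serious events". The only way back to SAE status within that criterion is an accompanying serious event. Whether PTX-35 caused the pain does not enter.

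Two other clauses of the same section matter here:
- Disease progression is also excluded, but SAE status returns "if the Investigator considers that there was a causal relationship between treatment with study drug or protocol design/procedures and the disease progression".
- Important medical events that meet none of the listed criteria "may be considered serious adverse drug events when, based on appropriate medical judgment". This is permission, not a requirement.

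The SAE label has two uses elsewhere in the plan:
- The second primary endpoint in section 9.2.1 is "Frequency of treatment-emergent adverse events (TEAEs) and serious adverse events (SAEs) related to PTX-35 during the trial".
- Section 8.1.2.6 requires notice of an SAE to the sponsor within 24 hours of the site learning of it.

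Hospitalization is treated differently in section 6.1.3. There, Grade 3 toxicities that are self-limited or medically controllable are not DLTs, but "such events are considered DLT if the abnormality leads to hospitalization".

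**The concern.** Read literally, the exclusion turns on the reason for admission. An admission for pain that the Investigator rates Possible or Definite under section 8.1.2.2 is not an SAE unless something else serious comes with it. The contrast with the progression clause suggests an omission, because that clause does bring drug-related cases back.

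Pain related to the drug is not far-fetched in this trial. This is a first-in-human study with no human safety data (section 2.6), and section 6.3 says "All patients should be observed for infusion-related reactions (e.g., back pain, fever and/or shaking chills", so back pain is named among the symptoms to expect.

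Two things are at stake. The related-SAE count, which is part of a primary endpoint, can be too low. And the only 24-hour reporting duty in the protocol may not apply to a drug-related admission.

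**Working it through.** No figure in the plan depends on this definition. The trial is descriptive and section 9.8 reports no sample size calculation, so there is nothing to reproduce. The check is a reading of the sections against each other, followed by arithmetic for scale only.

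**Step 1. Follow a related, pain-only admission through the protocol.** Assume that it is not life-threatening, fatal or disabling (otherwise another SAE criterion applies) and that no other serious event accompanies it.

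| Case | Related TEAE (8.1.2.1, 9.2.1) | DLT (6.1.3) | SAE by default (8.1.2.4) | Mandatory rapid notice |
|---|---|---|---|---|
| Grade 3, Cycles 1-2 | Yes | Yes, because it led to hospitalization | No | Yes, as a suspected DLT |
| Below Grade 3, Cycles 1-2 | Yes | Not by grade; only if judged unacceptable or if treatment has to be discontinued | No | None, unless a DLT is suspected |
| Grade 3, after 4 weeks | Yes | No, outside the window | No | None |
| Below Grade 3, after 4 weeks | Yes | No | No | None |

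The event is a recorded related TEAE in every row and an SAE by default in none. The first row has its own immediate route to the Medical Monitor or sponsor. The last two rows have no mandatory rapid route, and the second has one only if a DLT is suspected.

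**Step 2. Check whether other text closes the gap.**
- For events that meet DLT criteria after the window, section 6.1.3 asks for reporting as AEs or SAEs as applicable. This leads back to the definition in 8.1.2.4. It also says that these events are reviewed across cohorts to inform escalation.
- Under section 8.1.2.7.1 the Safety Review Committee (SRC) reviews serious and non-serious events as sites report them. This gives visibility, but sets no deadline.
- Section 12.1 asks only for timely submission of CRF data.
- The stopping criteria in section 5.5 cover possibly related deaths and two or more possibly related Grade 4 events. A single Grade 3 pain admission does not meet them.

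**Step 3. Scale of one event.** Inputs: the target of 22 to 34 patients (section 9.8) and 3 to 6 patients per dose level (Table 1). One event not counted lowers the related-SAE rate by 1/n:
- all patients: 1/22 = 4.5 points; 1/34 = 2.9 points
- one dose level: 1/3 = 33.3 points; 1/6 = 16.7 points

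Counting 0 instead of 1 moves the exact (Clopper-Pearson) 95% upper limit from 22.8% to 15.4% at n = 22, and from 15.3% to 10.3% at n = 34. The related-TEAE count does not change.

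**Step 4. Chance of at least one such event.** The documents give no rate p, so p is an assumption. The formula is 1 - (1 - p)^n.

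| Assumed p per patient | n = 22 | n = 34 |
|---|---|---|
| 1% | 19.8% | 28.9% |
| 2% | 35.9% | 49.7% |
| 5% | 67.6% | 82.5% |
| 10% | 90.2% | 97.2% |

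At 2% to 10% the expected number runs from 0.02 × 22 = 0.4 to 0.10 × 34 = 3.4.

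**The case against.** The case for leaving the text alone has several parts.

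- **The event is not lost.** All adverse events except minor laboratory abnormalities are recorded, so it stays in the related-TEAE count of the same primary endpoint. A Grade 3 pain admission in Cycles 1-2 also counts as a DLT, the other primary endpoint. This stands, and it limits the effect to the SAE component.
- **Escalation decisions do not rest on an SAE table.** The SRC reviews non-serious events too, may meet ad hoc, and considers late events that meet DLT criteria. This stands. A reader might infer that such admissions are hidden from escalation decisions; sections 6.1.3 and 8.1.2.7.1 say otherwise.
- **The Investigator can still call the event serious.** True, but the important-medical-event clause is discretionary and does not guarantee 24-hour notice.
- **Back pain during an infusion reaction would be an admission for the reaction, not for pain management.** This is a fair reading, and it weakens that example. The text does not say which reading applies, and it leaves other related pain uncovered.
- **A DLT that is not serious is no contradiction.** Correct. DLT status follows grade and timing, while seriousness follows outcome. The two treatments of hospitalization differ, but the definitions are not in conflict.
- **The scale figures are generic.** Also correct. The 1/n shift applies to any single event in cohorts of this size, and the event rates are assumed.

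**Conclusion.** The concern holds in a limited form. The pain, staging and catheter exclusion has no causality limit, so a PTX-35-related admission for pain alone is not an SAE by default. It leaves the related-SAE component of the second primary endpoint and the mandatory 24-hour notice. The gap is clearest after the 4-week DLT window, or earlier when DLT criteria are not met.

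One unclassified event is worth 2.9 to 4.5 points overall, or 17 to 33 points within a dose level. How many would occur cannot be derived from the documents. The conclusion assumes that sites apply the exclusion as written and do not use the important-medical-event clause.

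Two stronger readings are tempting but not supported. A reader might infer that these events drop out of the primary endpoint altogether, but they remain related TEAEs and some are DLTs. A reader might also infer that all rapid notice is lost, but a suspected DLT in Cycles 1-2 must be notified immediately. Nothing here calls for a change to the sample size or the analysis method.

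**What to change.** In section 8.1.2.4, limit the exclusion for pain management, staging and catheter placement to admissions that were pre-planned or are for events attributed as Unrelated under section 8.1.2.2. State that an unplanned admission for an event at least possibly related to PTX-35 is an SAE. This uses the existing attribution categories and parallels the progression clause. Align the SAE form instructions.

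The cost is about one sentence of protocol text, the form instructions and some additional SAE reports. These will include some tumour-pain admissions, because Unrelated is reserved for events that clearly have no link to treatment and Possible takes the doubtful ones. The related-SAE count may therefore rise through uncertain attribution as well as through true drug effects, and the report should say so.

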### **8.1.2.5 Pregnancy**

Any pregnancy detected during the study, or that occurs within 30 days after stopping study medication, must be reported immediately to the Investigator. Pregnancy, in and of itself, is not regarded as an adverse event, unless there is suspicion that study medication may have interfered with the effectiveness of a contraceptive medication. If the patient becomes pregnant while on-study, the study drug should be immediately discontinued. Pregnancy information about a female patient or a female partner of a male patient should be reported immediately from the time the Investigator first becomes aware of a pregnancy or its outcome. This will be performed by the Investigator per instructions from the Sponsor or its designee.

Any pregnancy complication, spontaneous abortion, elective termination of a pregnancy for medical reasons, outcome of stillbirth, congenital anomaly/birth defect, or serious adverse event in the mother will be recorded as an SAE and will be reported as described in Section [8.1.2.6](#).

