#### **4.4 End of Study**

The end of the study is defined as the date of the last visit of the last patient participating in the trial.

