## 5.0 SELECTION AND WITHDRAWAL OF PATIENTS

### 5.1 Inclusion Criteria

Patients **must** meet all of the following inclusion criteria before they will be allowed to participate in the trial:

1. Be willing and have the capacity to sign the written informed consent form.
2. Be male or female of at least 18 years of age at the time of signing informed consent.
3. Have a documented diagnosis of metastatic or advanced, unresectable solid tumor disease. Patient must have progressed or recurred following standard of care (SOC) therapies, or are ineligible for, or who refuse, other safe and effective SOC therapies, and whom the Investigator believes may benefit from experimental treatment with PTX-35.

4. Have an acceptable organ function, as defined below:
  - a. Albumin  $\geq$  2.5 g/dL
  - b. Total bilirubin  $< 3.0 \times$  upper limit of normal (ULN) unless patient has Gilbert's syndrome.
  - c. Alanine transaminase (ALT) and aspartate transaminase (AST)  $\leq 3.0 \times$  ULN, or  $\leq 5 \times$  ULN in the case of liver metastases.
  - d. Calculated or measured creatinine clearance  $> 35$  mL/minute per the Cockcroft-Gault formula.
  - e. Absolute neutrophil count  $\geq 1,500/\text{mm}^3$
  - f. Hemoglobin  $\geq 9$  g/dL.
  - g. Platelet count  $\geq 100,000/\text{mm}^3$
5. Have an Eastern Cooperative Oncology Group (ECOG) performance status of 0 to 2 ([APPENDIX I](#)).
6. Have life expectancy of at least three months.
7. Patients, both females and males, of childbearing/reproductive potential must agree to use adequate contraception, or continuous abstinence, while included in the trial and for six months after the last treatment with PTX-35.

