12. Have had a known tetanus/diphtheria vaccine within the past 10 years.
13. Have known additional malignancy that is active and/or progressive requiring treatment; exceptions include basal cell or squamous cell skin cancer, *in situ* cervical cancer, or other cancer for which the patient has been disease-free for at least two years.
14. Have known previously untreated or symptomatic metastases in the brain or spinal cord requiring steroids. Patients with treated and stable CNS metastases may be enrolled after approval of the sponsor and/or Medical Monitor.
15. Have any other ongoing significant, uncontrolled medical condition in the opinion of the Investigator.
16. Have known positive serology for human immunodeficiency virus (HIV), hepatitis B, or hepatitis C (except in cases of immunity after cured infection). Testing not required.
17. Have a history of substance abuse, medical, psychological or social conditions that may interfere with the patient's participation in the trial or evaluation of the trial result.
18. Be a female patient who is pregnant or breast feeding.

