### **5.4 Withdrawal Criteria**

Protocol therapy will be discontinued at any time if any of the following situations occur:

1. Progressive disease (not including unconfirmed radiographic PD if Investigator opts to continue treatment as outlined in section [8.2.1](#)).
2. Adverse event.
  - The development of toxicity which, in the Investigator's judgment, precludes further therapy.
  - Unacceptable adverse event(s).
  - Intercurrent illness that prevents further administration of treatment.
3. Withdrawal by subject.
4. Lost to follow-up.
5. Non-compliance.
6. At the discretion of the Investigator/physician decision.

7. Death.
8. Pregnancy.
9. Study termination.

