#### **5.4.1 Withdrawn Patients**

When a patient is removed from the study, the Investigator will clearly document the reason in the medical record and complete the appropriate case report form page describing the reason for discontinuation. In addition, every effort should be made to complete the appropriate assessments listed in Section [7.4](#).

Patients lost to follow-up will be withdrawn from the study. Patients will be declared “lost to follow-up” if the last contact date has exceeded two years, and/or the site has documented three attempts to contact the patient by telephone and/or certified letter to last known address.

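### Pregnancy reporting names 30 days after stopping drug while contraception runs six months, and no scheduled contact after the last dose asks about pregnancy (minor safety alignment)

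*Combined protocol and SAP*

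**What the plan says.** Two periods after the last dose bear on pregnancy.

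- **Contraception.** Inclusion criterion 7 (Synopsis and Section 5.1) requires patients of either sex with reproductive potential to use contraception or remain abstinent "while included in the trial and for six months after the last treatment with PTX-35".
- **Reporting.** Section 8.1.2.5: "Any pregnancy detected during the study, or that occurs within 30 days after stopping study medication, must be reported immediately to the Investigator". A later sentence in that section covers the Investigator's own report. Information on a pregnant patient, or on the pregnant partner of a male patient, "should be reported immediately from the time the Investigator first becomes aware of a pregnancy or its outcome". No day count is attached to that sentence.

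Section 8.1.2.5 also states: "Pregnancy, in and of itself, is not regarded as an adverse event", except where the drug is suspected of having interfered with a contraceptive. Pregnancy complications and adverse outcomes, by contrast, are recorded as SAEs.

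Pregnancy is checked before treatment. Exclusion criterion 18 reads "Be a female patient who is pregnant or breast feeding", Table 2 note i requires a negative test in the 7 days before the first dose for women of childbearing potential, and eligibility is confirmed again on Cycle 1 Day 1. During treatment, pregnancy is the eighth entry in the Section 5.4 list, which opens "Protocol therapy will be discontinued at any time if any of the following situations occur".

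**The concern.** The sponsor's own criterion treats the six months after the last dose as a period in which pregnancy should be avoided. One would expect the pregnancy-reporting clause to name the same period and the follow-up contacts to ask about it. The clause names 30 days, and the contact lists do not mention pregnancy.

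At stake is safety information. PTX-35 has not been given to humans before, and Section 2.6 says that no human safety data exist. If a patient or a partner becomes pregnant after the first month off drug but within the contraception period, the site may not hear of it. The outcomes that 8.1.2.5 wants recorded as SAEs, such as spontaneous abortion, stillbirth or congenital anomaly, would then be missed too. There would be few such events, but each would be informative.

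**Working it through.** The protocol states no figure to reproduce on this point. The check compares texts, with one small count.

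**1. Is 30 days a cap on reporting?** No. The first sentence of 8.1.2.5 has two alternatives joined by *or*: found while the study is running, or occurring within 30 days of stopping drug. The first has no day limit and may reach well into follow-up:

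- Section 4.4: "The end of the study is defined as the date of the last visit of the last patient participating in the trial".
- Table 2 note r has survival contacts running until death.
- Section 5.4.1: "Patients lost to follow-up will be withdrawn from the study". This implies that patients still being followed remain in the study.

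On that reading the 30-day alternative adds little. On a narrower reading, where the study ends for a patient when treatment ends, it is the operative limit. The text does not say which is meant. Either way, the Investigator's onward report is triggered by awareness, without a time limit.

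**2. Would the site become aware?** The lists that apply after the last dose are:

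| Section | Timing | What is collected that could bring a pregnancy to light | Pregnancy test or question |
|---|---|---|---|
| 7.4 | 30 ± 3 days after last dose | Physical exam, laboratory tests, AE assessment, medication review | None |
| 7.5 | Every 8 weeks until progression | Imaging, later cancer therapy, PTX-35-related AEs only | None |
| 7.6 | About every 12 weeks until death | Survival status, later cancer therapy | None |

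Count: 0 of 3. The AE line does not by itself call for pregnancy, because an uncomplicated pregnancy is not classed as an AE. The 30-day visit can fall on day 30 − 3 = 27, before even the 30-day period has closed.

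**3. Testing.** Table 2 and Section 7.2 contain one pregnancy test, before the first dose. The Day 1 lists for Cycle 2 onward (Sections 7.3.3 and 7.3.4) have no test or question, so the rule to stop drug on pregnancy also relies on the patient volunteering the information.

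**4. Can existing contacts cover six months?** Take six months as about 26 weeks and count contacts from the last dose (an assumption, since 7.5 counts from the last scan and 7.6 from progression or new therapy).

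- 8-weekly: 26/8 = 3.25, so the fourth contact (week 32) is the first after six months.
- 12-weekly: 26/12 = 2.2, so the third contact (week 36) is the first after six months.

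With the 30-day visit, that is about 1 + 3 = 4 to 1 + 4 = 5 questions per patient, with no added visit.

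**The case against.** The other side has four good arguments.

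**Later pregnancies are already reportable.** This stands. A reader might subtract 30 days from six months and conclude that about five months go unreported. The documents do not support that. The 30 days is one alternative in an either-or sentence, the other alternative may cover the whole of follow-up, and the Investigator must report on awareness with no day limit. The difference between the two periods does not measure unreported time.

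**Thirty days fits the protocol's safety framework.** The 30-day visit, the collection of all SAEs regardless of cause (Section 8.1.2.6) and the switch to related AEs only (Table 2 note q) all use 30 days. A contraception period limits exposure, whereas a reporting period governs data collection, and nothing in the documents requires the two to be equal. This explains where 30 days probably comes from and makes the matter one of alignment. It does not tell the site how it would learn of a pregnancy in the remaining months.

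**The consent form may instruct patients.** It may, and so may the Sponsor's pregnancy instructions mentioned in 8.1.2.5. Neither is available here, so the point concerns the protocol text only.

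**The site is in regular contact with patients anyway.** Physical examinations are listed on Day 1 of each cycle and at the 30-day visit, and Section 8.1.2.1 has patients interviewed in a non-directed way at each evaluation. A pregnancy could well come up. Survival contacts, however, may be by telephone or electronic message and are limited to vital status and therapy. No list provides for contact with a male patient's partner.

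**Conclusion.** The point holds as a minor safety alignment, at the lowest level of severity. The only numeric post-dose pregnancy period is 30 days against a six-month contraception requirement. It is unclear how far the study-duration alternative extends, and 0 of the 3 lists that apply after the last dose ask about pregnancy. Within the protocol text, finding out depends on unprompted disclosure.

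This does not mean that pregnancies after day 30 are excluded from reporting, or that any known share of them would be missed. The documents give no pregnancy rate. Few events are to be expected in 22 to 34 patients with advanced cancer who must use contraception or abstain. No endpoint, dose-escalation decision or sample size is affected.

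The conclusion assumes that the consent form and the Sponsor's instructions do not already ask patients to report pregnancy for six months. If they do, only the wording of 8.1.2.5 needs attention.

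**What to change.** 1. In Section 8.1.2.5, replace the 30-day limit with six months after the last dose of PTX-35, and state that it applies to female patients and to female partners of male patients.
2. Add one pregnancy question to the 30-day visit (7.4) and to the planned 8-weekly (7.5) or 12-weekly (7.6) contacts, up to and including the first contact after six months. Mark it in Table 2.
3. Optionally, add the same question on Day 1 of Cycle 2 onward (7.3.3, 7.3.4), to support the existing rule to stop drug on pregnancy.

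The cost is one changed clause, a line in the affected visit lists and Table 2, and about four or five short questions per patient after the last dose. Any pregnancy found will need outcome follow-up, with the partner's consent where it is a partner's pregnancy. No visit or procedure is added.
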